- Beginning at Cycle 4, collect a sample at predose Day 1 and then predose every 3 cycles (Cycles 7, 10, etc.); at the EOT visit, and at the first posttreatment visit.

Note: Ten subjects enrolled in Part 1 completed serial pharmacokinetic sampling before implementation of Amendment 2. The time points for serial PK sampling are provided in Amendment 1.

Table 3: Time and Events Schedule for Part 2 Main Study (Double-blind, Randomized 2:1, Imetelstat or Placebo Treatment)

Study Procedures	Comments	PHASE	Screening Phase	Treatment Phase (4-week cycles ± 3 days)					Posttreatment Follow-up Phase
				Up to 28 days before Randomization	Cycle 1 Day 1 (predose)	Cycle 1 Day 8, 15, 22	Cycle 2 Day 1, 8, 15, 22	Cycle 3 until EOT Day 1	
Screening									
Informed consent	Refer to Section 9.1.3 for guidance regarding COVID-19 and further clarification of screening procedures.		X						
Inclusion/exclusion criteria			X	X					
Medical history and demographics			X						
Study Medication Administration									
Randomization	Randomization will occur on C1D1 or up to 72h prior to study drug administration			X					
Dispense/administer study drug	Refers to Imetelstat or placebo (see Section 6). The screening weight is considered baseline for dose calculation. Recalculate dose if $\geq 10\%$ weight change from baseline. Dosing should begin within 72 hours of randomization in IWRS.			X		X (D1 only)	X		
Safety Assessments									
Physical exam (including weight)	Full PE at Screening; limited symptom-directed PE thereafter. Refer to Section 9.8.4 for guidance regarding COVID-19.		X	X		X (D1 only)	X	X	
Vital signs	Includes temperature, HR, SBP and DBP (preferably in a seated position). Measured and recorded prior to infusion.		X	X		X (D1 only)	X	X	
12-lead ECG	At screening, at C2D1 and as clinically indicated.		X			X (D1 only)			
Efficacy Assessments									
Transfusion history and status; myeloid growth factor treatment	Assessment of RBC transfusion requirement 16 weeks prior to Randomization and at each clinic visit until the end of treatment. Sites should make every attempt to obtain complete information, including both in-patient and out-patient transfusions (see Section 9.3.1.1 for additional information). Pre-transfusion Hb must be documented. Note: if DE Visit does not align with a Cycle Day 1 visit, then transfusion data must be collected at the DE Visit.		X	X		X (D1 only)	X	X	
								X (every 4-6 weeks) until first transfusion in Posttreatment follow-up	

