6.1.1. Dose Modifications for Hematologic Toxicities

For any occurrence of Grade ≥ 3 thrombocytopenia or neutropenia, additional weekly blood counts should be performed until there is a return to baseline values. For treatment of hematologic toxicities, granulocyte-colony stimulating factors (G-CSF) are permitted for neutropenia as well as blood transfusions for anemia or thrombocytopenia.

The actions in Table 7 should be taken for Grade 3 hematologic toxicities present at the planned start of a dosing cycle. The actions in Table 8 should be taken for imetelstat-related Grade 4 hematologic toxicities at the planned start of a dosing cycle. It is recommended to contact the sponsor before discontinuing treatment due to Grade 3 or Grade 4 hematologic toxicity, particularly when the hematologic toxicity is without clinical consequences. Note that for Grade 3 or Grade 4 hematologic toxicities that are not considered related to imetelstat, the dose should still be held until recovery to ANC $1 \times 10^9/L$ and platelets $50 \times 10^9/L$.

Table 7: Dose Modifications for Grade 3 Hematologic Toxicities

Occurrence	Action
First	Hold study drug until recovery to ANC $1.0 \times 10^9/L$ and platelets $50 \times 10^9/L^*$; may restart at most recent dose level
Second	Hold study drug until recovery to ANC $1.0 \times 10^9/L$ and platelets $50 \times 10^9/L^*$; restart at 1 dose level lower
Third	Hold study drug until recovery to ANC $1.0 \times 10^9/L$ and platelets $50 \times 10^9/L^*$; restart at 1 dose level lower
Fourth	Discontinue study drug**

*For any other hematologic toxicities, the minimum counts for restarting should be at the Investigator's discretion

** Contact the sponsor to discuss the specific case before study drug is discontinued for hematologic toxicity

Table 8: Dose Modifications for Grade 4 Hematologic Toxicities

Occurrence	Action
First	Hold study drug until recovery to ANC $1.0 \times 10^9/L$ and platelets $50 \times 10^9/L^*$; restart at 1 dose level lower
Second	Hold study drug until recovery to ANC $1.0 \times 10^9/L$ and platelets $50 \times 10^9/L^*$; restart at 1 dose level lower
Third	Discontinue study drug**

*For any other hematologic toxicities, the minimum counts for restarting should be at the Investigator's discretion

** Contact the sponsor to discuss the specific case before study drug is discontinued for hematologic toxicity

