subject into the study. Over the course of the study, concomitant therapy may need to be adjusted based on the subject's clinical status. Subjects receiving iron chelating agents should be assessed regularly for the need for dose reductions and/or continued use of iron chelating agents according to local prescribing information (eg, hold dose for ferritin levels <500 mcg/L) in order to reduce the potential risk of hepatic toxicity. Concomitant therapies should be recorded beyond 30 days only in conjunction with new or worsening adverse events or serious adverse events that meet the criteria outlined in Section 12.3.2, Serious Adverse Events.

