9.1.5. Posttreatment Phase (Follow-Up)

The Posttreatment Follow-up Phase is the time between the End-of-Treatment Visit and the end of study participation or end of study. During this phase, contact will be made as detailed in the Time and Events Schedules (Table 1 and Table 3) until the subject has died, is lost to follow-up, or has withdrawn consent.

If study drug is discontinued for any reason other than disease progression, a response assessment should be performed at the time of suspected disease progression.

Collection of transfusion data should continue every 4 to 6 weeks until the first transfusion in the posttreatment follow-up phase.

If the information on survival status and subsequent therapy is obtained via telephone contact, then written documentation of the communication must be available for review in the source documents. If the subject has died, then the date and cause of death will be collected and documented on the eCRF. Where allowed by local law, public records may be used to document death for the purpose of obtaining survival status.

As per the Time and Events Schedule for the main study of Part 2 (Table 3), sites should attempt to administer the PRO questionnaires before any tests, procedures, or other consultations are

performed, when possible, (see Section 9.6). Subjects who visit the site for the follow-up assessments should complete the questionnaires at that time. If the assessments are conducted via a telephone call with the subject, then the subject's questionnaire responses will be read over the telephone to the site staff who will record the data in the questionnaires. If the subject is unable to complete the assessments during the Posttreatment Follow-up Phase, then the reason for not completing the questionnaires will be documented (eg, too ill, subject refused). Subjects will be required to complete PRO questionnaires in posttreatment follow-up until the start of subsequent therapy.

The sponsor will ensure that subjects benefiting from treatment with imetelstat will be able to continue treatment after the End of the Study. Subjects who were assigned to the placebo arm in the main study will be instructed that they should return to their primary physician to determine standard of care.

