9.3.1.1. Transfusions

Transfusion data will be collected during the treatment and posttreatment periods throughout the study as specified in the Time and Event Schedules. Transfusion is monitored at each visit for imetelstat infusion (every 4-week cycle), at each disease evaluation visit, and at all unscheduled visits during treatment. During the posttreatment phase, transfusion data will be collected every 4 to 6 weeks until the first transfusion in follow-up. Enhanced operational monitoring will be implemented to seek transfusion information from other documented sources. Enhanced and continuous medical review will be implemented to identify any sudden but unsustained increase of Hb values and to query whether transfusion has occurred.

Data to be collected include the date of transfusion, number of units and type of blood products transfused and the pre-transfusion Hb and platelet count. Red blood cell transfusions may be administered based on Hb level, investigator's assessment of the subject's clinical signs and symptoms, and local clinical practice. As the volume of 1 unit of RBC transfusion may vary regionally, one unit is defined as the amount that is intended to raise Hb by approximately 1 g/dL

in an adult patient (ie, one standard pRBC unit or equivalent). The total number of RBC units required over rolling 8-week time periods will be calculated to identify subjects who achieve RBC TI or transfusion reduction.

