4.9.1.1 Handling of Missing Data

No imputations for missing data will be made for the primary and secondary efficacy endpoints. The double-blind study design of Part 2 and the symmetric assessment schedule reduce the potential for systematic bias, but the treatment effect may be attenuated by missing transfusion data. In order to be considered transfusion independent, a subject must have completed continuous transfusion assessments throughout the qualifying observation period where his/her transfusion independence is determined. An apparent transfusion free period with one or more missing transfusion assessments will not be considered a qualifying 8-week or 24-week TI period. Subjects with no qualifying observation periods will be considered non-responders.

The number and percentage of subjects with missing data for the primary endpoint will also be summarized by major reason. In addition, a Kaplan-Meier plot of the time to study discontinuation will be provided.

A subject data listing will be provided showing all subjects with missing values for the primary endpoint. For these subjects, the listing will provide the observed data relating to the primary endpoint, important baseline characteristics, the recorded reason(s) for study discontinuation and the timing of study discontinuation.

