4.9.3 Key Secondary Efficacy Variables

4.9.3.1 Variables Definition

24-week RBC TI rate

24-week RBC TI rate is defined as the proportion of subjects without any RBC transfusion during any consecutive 24 weeks (168 days) starting from Study Day 1 until subsequent anti-cancer therapy if any. The starting date of 24-week RBC TI must be between Study Day 1 and the date of last dose of study drug + 30 days or End of Treatment Visit whichever occurs first, or Study Day 31 if randomized but not treated.

Time to 8-week (24-week) RBC TI

Time to 8-week (24-week) RBC TI is defined as the interval from Study Day 1 to the first day of the first 8-week (24-week) RBC TI period.

Duration of RBC TI

Duration of RBC TI is defined as the first day of the longest RBC TI period to the date of the first RBC transfusion after the TI period starts. Subjects who have not had an RBC transfusion ending the TI period at the time of analysis or who withdraw from the study will be censored at the date of the last transfusion evaluation or the day before the first date of subsequent anticancer therapy if given, whichever occurs first.

Rate of hematologic improvement, including HI-E, per modified IWG 2006

The modified IWG 2006 criteria [5] for HI define specific responses of cytopenia in the three hematopoietic lineages: erythroid (HI-E), platelet (HI-P), and neutrophil (HI-N). Rate of hematologic improvement is defined as the proportion of subjects who achieve HI-E, or HI-P, or HI-N.

HI-E is defined as a hemoglobin (Hb) increase of at least 1.5 g/dL above pretreatment and lasts at least 8 weeks or reduction of at least 4 units of RBC transfusion units/8 weeks compared with the prior RBC transfusion burden. A valid 8-week period must start before the date of last dose of study drug + 30 days or End of Treatment Visit whichever occurs first, or Study Day 31 if randomized but not treated, and ends before the first transfusion in posttreatment follow-up or the first day of subsequent anti-cancer therapy whichever occurs first. Pretreatment Hb level is defined as the average of all the Hb values (from transfusion history, local, and central lab) in the 8 weeks prior to first dose date, including the value on first dose date (Part 1 or Part 2) and excluding values that were within 14 days after transfusion (thus considered to be influenced by transfusion) for all

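### Off-drug transfusion collection and the SAP's HI-E and RBC-amount windows end at a first transfusion not limited to RBCs, so a platelet unit after the End of Treatment visit can close an RBC-defined window

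*Protocol*

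**What the plan says.** **Collection.** Protocol 9.1.5 states: "Collection of transfusion data should continue every 4 to 6 weeks until the first transfusion in the posttreatment follow-up phase". Protocol 9.3.1.1 states: "During the posttreatment phase, transfusion data will be collected every 4 to 6 weeks until the first transfusion in follow-up". The transfusion row of Table 3 ends collection with the words "until first transfusion in Posttreatment follow-up". Table 5 uses an equivalent rule in the Extension Phase.

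**Scope of the data.** Protocol 9.3.1.1 states: "Data to be collected include the date of transfusion, number of units and type of blood products transfused", and it also asks for the pre-transfusion platelet count. Protocol 6.1.1 permits growth factors for neutropenia "as well as blood transfusions for anemia or thrombocytopenia".

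**Analysis.** SAP 4.9.2.1 and 4.9.3.1 define 8-week and 24-week TI by the absence of RBC transfusion for 56 or 168 days. The window may start as late as last dose + 30 days or the EOT visit, whichever is first, so it can run well into follow-up. SAP 4.9.1.1 states: "An apparent transfusion free period with one or more missing transfusion assessments will not be considered a qualifying 8-week or 24-week TI period". A subject with no qualifying period is a non-responder. For HI-E, SAP 4.9.3.1 requires an 8-week period that "ends before the first transfusion in posttreatment follow-up or the first day of subsequent anti-cancer therapy whichever occurs first". The 8-week and 16-week RBC-amount intervals carry the same end rule. Duration of RBC TI ends at the first RBC transfusion, but without one it is censored at the last transfusion evaluation or the day before subsequent therapy.

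**The concern.** The event that stops data collection is wider than the event the endpoints count. A subject who stops study drug while free of RBC transfusion, and who then receives platelets, has had nothing happen that bears on RBC transfusion independence. Under the literal wording, collection stops all the same.

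The SAP turns that stop into an outcome. For TI it works through the missing-assessment rule. For HI-E and RBC amounts it is part of the window definition. The endpoints exposed are the primary endpoint (8-week TI) and the two gatekeepers, 24-week TI and HI-E, which must both succeed before PFS and OS are tested (SAP 4.9.1.3). TI duration may be censored early as well.

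Protocol 1.1.5.2.1 describes thrombocytopenia as dose-limiting for imetelstat, so the loss could fall unevenly between arms.

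**Working it through.** **1. Wording side by side**

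| Place | Event named | Limited to RBC? |
|---|---|---|
| Protocol 9.1.5, 9.3.1.1, Table 3: stop of off-drug collection | first transfusion | No |
| SAP 4.9.3.1: HI-E and RBC-amount windows | first posttreatment transfusion | No |
| SAP 4.9.2.1, 4.9.3.1: 8-week and 24-week TI | RBC transfusion | Yes |
| SAP 4.9.3.1: end of TI duration | first RBC transfusion | Yes |

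The SAP names RBCs in some rules and omits them in others within the same section. Table 1 (Part 1) has a backstop of at least 12 months of transfusion data for subjects who stop early. Table 3 has none.

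**2. Timing**

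A window that opens on the EOT visit needs 56 further days for 8-week TI or 168 for 24-week TI. Contacts come every 28 to 42 days. That means up to two contacts for 8-week TI (56/28 = 2) and four to six for 24-week TI (168/42 = 4; 168/28 = 6).

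Illustrative subject, with Day 0 as the last dose: RBC-free from Day -10, EOT visit on Day 30, platelets on Day 40, no RBCs, no earlier qualifying window. The next contact falls between Day 30 + 28 = 58 and Day 30 + 42 = 72.

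- 8-week TI is complete on Day -10 + 56 = 46. On Day 40 only 50 days have accrued. If the site stops at the platelet date, the window is incomplete. If it records RBC status up to the next contact, the window completes.
- HI-E must end before Day 40, but this period ends on Day 46, so it is closed by definition whatever data exist. A valid period would have had to open before Day 40 - 56 = Day -16.
- 24-week TI is complete on Day -10 + 168 = 158. Even with recording up to the next contact, 158 - 72 = 86 to 158 - 58 = 100 days are unobserved, so the window does not qualify.

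**3. The plan's own power figure**

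Inputs (Protocol 11.3): 30% versus 7.5%, two-sided 0.05, continuity-corrected chi-square, 150 subjects at 2:1 (100 and 50).

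- Pooled rate = (100 × 0.30 + 50 × 0.075)/150 = 0.225
- Null SE = √[0.225 × 0.775 × (1/100 + 1/50)] = 0.0723
- Alternative SE = √[0.30 × 0.70/100 + 0.075 × 0.925/50] = 0.0591
- Continuity correction = 0.5 × (1/100 + 1/50) = 0.015
- z = (0.225 - 0.015 - 1.96 × 0.0723)/0.0591 ≈ 1.16, giving power 87.6%

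Exact enumeration gives 88.7%. The stated 88% is reproduced and is not in dispute.

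**4. What a lost responder costs**

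One imetelstat subject is 1/115 = 0.87 points. Expected 8-week responders are 115 × 0.30 = 34.5. The same formula at 115 and 55, with placebo held at 7.5%, gives:

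| Imetelstat responders lost (assumed) | Rate | Power |
|---|---|---|
| 0 | 30.0% | 91.7% |
| 1 | 29.1% | 89.6% |
| 3 | 27.4% | 84.1% |
| 5 | 25.7% | 77.1% |

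The number lost is an assumption. The documents give no rate of platelet transfusion after EOT, so the table shows sensitivity only.

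**The case against.** **The wording is ambiguous rather than plainly wrong.** A reader might infer that the plan instructs sites to stop at a transfusion of any product. It does not say so. The Table 3 comment opens with the RBC transfusion requirement, and 9.3.1.1 says the data serve to total RBC units, so some sites will read the rule as RBC only. This stands, but it leaves collection dependent on each site's reading and does not touch the SAP window definitions.

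**Most drug-related thrombocytopenia may be over by then.** Protocol 1.1.5.2.1 says most Part 1 cytopenias resolved in about 4 weeks, and follow-up begins only at the EOT visit, 30 ± 3 days after the last dose. Platelets given before that visit do not trigger the rule. The Part 1 figure of 31/57 (54.4%) counts Grade 3 or higher thrombocytopenia at any time; it is not a platelet-transfusion rate. This stands: a loss concentrated in the imetelstat arm is plausible but unproven.

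**Few subjects can change status.** Anyone with an earlier qualifying window is already a responder. Nor is anyone misclassified who would have needed RBCs or started subsequent therapy before completing the window. This also stands.

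**Other tempting readings.** Protocol 8.3 limits concomitant-therapy recording after 30 days: "Concomitant therapies should be recorded beyond 30 days only in conjunction with new or worsening adverse events" or serious adverse events. A reader might infer that sites would stop recording transfusions at Day 30. The separate Table 3 row, 9.1.5 and 9.3.1.1 give a more specific schedule, which should govern; a cross-reference is all that is missing. A reader might also count Table 5 as a source of bias. The Extension Phase starts 24 months after the last randomization, when the final main-study analysis is planned, so it cannot affect these endpoints.

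**Direction.** SAP 4.9.1.1 already accepts that missing transfusion data may attenuate the effect, and requiring continuous assessment is a deliberate choice. That defends the missing-data rule, but not a collection rule that creates missing data for a reason unrelated to RBCs.

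**Conclusion.** The point holds as a mismatch between the stopping event and the RBC-defined endpoints. On a literal reading, a platelet transfusion after EOT always closes the HI-E and RBC-amount windows. It readily defeats a 24-week TI window that crosses EOT. It can defeat an 8-week window, depending on whether the site records up to the transfusion or up to the next contact. TI duration may also be censored early.

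The size cannot be derived from the documents beyond 0.87 points per affected imetelstat subject, and only subjects with no earlier qualifying window count. A claim that the rule does bias the primary endpoint and both gatekeepers against imetelstat goes further than the documents allow. It would need post-EOT platelet transfusion to be more common on imetelstat and enough subjects to have a deciding window open at EOT. If those conditions hold, the treatment effect is attenuated; type I error for a claim of benefit is not inflated. The correction is worth making because it is nearly free and two of the exposed endpoints are gatekeepers.

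**What to change.** - In Protocol 9.1.5, 9.3.1.1 and Table 3, replace first transfusion with first RBC transfusion. Change Table 5 too, for consistency only.
- In SAP 4.9.3.1, make the same change in the end rule for the HI-E window and for the 8-week and 16-week RBC-amount intervals.
- In Protocol 8.3, add a cross-reference stating that posttreatment recording of transfusions and myeloid growth factors follows 9.1.5 and Table 3.

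The cost is a wording change in both documents and a few extra contacts, every 4 to 6 weeks, for subjects who received platelets but no RBCs after EOT.

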9.1.6. Extension Phase

Subjects benefiting from imetelstat treatment at the end of the main study (ie, 24 months after last subject randomized in the main study of Part 2) per investigator assessment may continue to receive imetelstat during the Extension Phase. Subjects in the Posttreatment Follow-up Phase of the main study will also continue in the Extension Phase for extended follow-up for assessment of survival status, subsequent anticancer therapy, and monitoring of disease progression, including progression to AML (Table 5). Subjects will be followed in the Extension Phase for at least 5 years from the first dose of imetelstat received in Part 2 of the main study (including treatment and follow-up), or 3 years of post-treatment follow-up from the last dose of study treatment, whichever occurs later, or until death, withdrawal of consent, study termination, or until a subject is lost to follow-up. During the Extension Phase, the Independent HEC will be available to review all hepatic adverse events and liver function test abnormalities at least on a quarterly basis, or more frequently if needed.

Imetelstat-treated subjects in the QTc substudy may also enter the Extension Phase after the clinical cut off for the primary analysis is reached for the substudy. The end of study for the QTc substudy subjects will be when the subjects from the main study complete the Extension Phase.

Prior to entering the Extension Phase, subjects must sign and date an updated ICF. After sponsor communication of the completion of the main study, the Extension Phase will begin and subjects will follow the Time and Events Schedule for the Extension Phase (Table 5). All requirements for administration of imetelstat, including guidelines for dose modification, will continue during the Extension Phase (see Section 6). Treatment may continue until there is loss of benefit or unacceptable toxicity, as determined by the investigator according to local standard of care, or end of the Extension Phase.

Subjects who discontinue imetelstat during the Extension Phase, or who have already discontinued study treatment before entering the Extension Phase, will be contacted to determine survival status and disease progression, including progression to AML every 16 weeks \pm 7 days (from the EOT

visit date) until the Extension Phase ends. Procedures for documentation of survival follow-up are described in Section 9.1.5.

